6.2 Efficacy Assessments

Efficacy assessments will be collected through a paper diary, which will be used to record emetic episodes and use of rescue medication. An emetic episode is defined as one or more continuous vomits (expulsion of stomach contents through the mouth) or retches (an attempt to vomit that is not productive of stomach contents). Regurgitation (defined as the sudden effortless return of small volumes of gastric contents into the pharynx and mouth – typically after breastfeeding or bottle feeding) is a physiological event and must not be considered as an emetic episode (for patients up to 12 months of age). Patients, parents/guardians or caregivers should complete the diaries. Instructions on how to compile the paper diary will be given at the Screening Visit (Visit 1). Paper diary will be distributed at Day 1 (Visit 2) and will be collected at Final Visit (Visit 4).

6.2.1 Primary Endpoint

PK/PD relationship between netupitant exposure (AUC, C_{max}) and antiemetic efficacy in the delayed phase after a single oral netupitant administration, concomitantly with oral palonosetron, in pediatric cancer patients receiving HEC or MEC treatments. Efficacy parameter to be used in the correlation is the proportion of patients with CR (i.e., no emetic episodes and no rescue medication) during the delayed phase (> 24-120 h after the start of chemotherapy on Day 1).

6.2.2 Secondary Endpoints

- Pharmacokinetic (PK) endpoints:
 - AUC, C_{max} , t_{max} and $t_{1/2}$ of netupitant, netupitant metabolites M1, M2, M3, and palonosetron.
- Pharmacodynamic (PD) endpoints:
 - proportion of patients with complete response (CR, i.e., no emetic episodes and no rescue medication) during the delayed (> 24-120 h), acute (0-24 h), and overall phases (0-120 h) after start of chemotherapy administration on Day 1.
 - proportion of patients with no emetic episodes during the delayed (> 24-120 h), acute (0-24 h), and overall phases (0-120 h) after start of chemotherapy administration on Day 1.

Clinical Study Protocol

• proportion of patients with no rescue medication during the delayed (> 24-120 h), acute (0-24 h), and overall phases (0-120 h) after start of chemotherapy administration on Day 1.

6.3 Safety Assessments

Safety assessments will consist of full physical examination (PE) and clinical laboratory tests (serum chemistry, hematology, urinalysis): these assessments will be performed at screening and at final visit (Visit 4). Moreover, vital signs measurements (pulse rate, systolic and diastolic blood pressure) and 12-lead ECGs (single recordings) will be obtained at screening, on Day 1 at 4-6 h after study drug administration, and at final visit.

Adverse events (AEs) will be monitored throughout the study.

6.3.1 Physical Examination

A full physical examination will be performed at Visit 1 (screening) and Visit 4 (Day 6, 7 or 8). This evaluation will include an examination of general appearance, head, eyes, ears, nose, throat, skin, neck, lungs, cardiovascular, breast, lymph nodes, abdomen, musculoskeletal and neurological. Information about the physical examination will be recorded in the source documentation at the site and in the eCRF. Significant findings/illnesses, discovered after the first study drug administration and which meet the definition of an AE, will also be recorded in the eCRF.

6.3.2 Vital Signs

Vital signs assessments will include: pulse rate, systolic and diastolic blood pressure, height/length (only at Visit 1, screening), and body weight (at Visit 1 and Visit 2). Pulse rate, systolic and diastolic blood pressure will be measured after the patient has been in the sitting or lying position for at least 5 minutes at Visit 1 (screening), Visit 2 (4-6 h after study drugs administration; Day 1) and Visit 4 (Final visit, Day 6, 7 or 8).

Vital signs shall be measured before PK sampling or at least 30 minutes after PK sampling.

6.3.3 12-lead ECG

Twelve-lead ECGs (single recording) will be recorded for each patient at Visit 1 (screening), Visit 2 at 4-6 h after study drugs administration, and Visit 4 (Day 6, 7 or 8, final visit). A digitally recorded ECG will be transmitted from the study site to a central reading facility, where ECG interpretations will be timely performed by a cardiologist (in case cardiologist's report is pending, the assessment of compliance with exclusion criterion #21 could be made based on automatic interpretation of QTcB and QTcF results by ECG machine at the discretion of Investigator). ECG interpretation scheme will include the analysis of the morphology, rhythm, conduction, ST segment, PR, QRS, QT and QTc intervals, T waves, U waves and the presence or absence of any pathological changes. The investigator will receive more detailed information regarding the ECG recording and assessment procedures in a separate manual.

After review of the results received from the central reading facility, the investigator must sign and date each ECG report.

ECGs shall be obtained before PK sampling or at least 30 minutes after PK sampling.

6.3.4 Clinical Laboratory Tests

The following parameters will be assessed at Visit 1 (screening) and Visit 4 (final visit):

- a) Hematology: hematocrit, hemoglobin, erythrocytes (RBC), platelets, leukocytes (WBC), neutrophils, lymphocytes, basophils, eosinophils, monocytes.
- b) Blood Chemistry: urea, creatinine/eGFR, total bilirubin, alkaline phosphatase (ALP), alanine aminotransferase (ALT), aspartate aminotransferase (AST), sodium, potassium, albumin, total protein, blood glucose and total creatine kinase (CK).
- c) Urinalysis: protein, glucose, WBC, RBC, and bacteria.

Female patients having reached menarche will have to undergo a urine pregnancy test at screening and on Day 1, as well as a blood pregnancy test on Visit 4 (final visit) as part of the clinical laboratory assessments.

All blood and urine samples collected at Visit 1 and Visit 4 will be sent to a central laboratory for analysis. Local laboratory results obtained from an appropriately certified local laboratory within the screening period could be used to support eligibility criteria at the discretion of Investigator. Only the confirmation of eligibility will be recorded in the eCRF as local laboratory values will not be entered into the eCRF.

After review of the results received from the central laboratory, the investigator must sign and date each laboratory report. The laboratory will provide normal reference ranges for the laboratory results report and will flag all abnormal values. The investigator will consider the values outside the normal range and repeat the test, if needed. In case clinically significant laboratory abnormalities are assessed by the Investigator, the etiology of the abnormality should be identified and the diagnosis should be recorded as an AE. Otherwise, if the etiology cannot be identified, the laboratory abnormality as such should be recorded as AE.

Clinically significant laboratory abnormalities (including those values \geq grade 3 severity) detected after screening, if not justified by an underlying disease already recorded in the medical history, are to be recorded as AEs.

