7 ADVERSE EVENTS

7.1 Method of Assessment

7.1.1 Definition of Adverse Events

Adverse Event (AE)

As defined by the current ICH Guideline for Good Clinical Practice [27] an Adverse Event (AE) is:

Any untoward medical occurrence in a patient or clinical investigation subject administered a pharmaceutical product and which does not necessarily have to have a causal relationship with this treatment. An AE can therefore be any unfavorable and unintended sign (including an abnormal laboratory finding), symptom, or disease temporally associated with the use of a medicinal (investigational) product, whether or not considered related to the medicinal (investigational) product.

Within the scope of this study, such untoward medical occurrences would be considered as "AEs" even if the subject was not administered the study drugs but the subject (and/or subject's parent/guardian, as applicable) had already signed the Informed Consent/Assent Form.

This definition includes intercurrent illnesses or injuries, exacerbation of pre-existing conditions, and adverse events occurring as a result of drug withdrawal, abuse, medication errors, misuse or overdose. Adverse events observed during all periods of a clinical trial are to be recorded, including adverse events occurring during a period without trial medication.

Planned surgical interventions or planned hospitalizations scheduled prior to the Informed Consent but performed during the study should not be considered (serious) AEs.

Signs and symptoms considered as lack of efficacy (nausea and vomiting) and occurring during the study up to 5 days after the study drugs administration, will not be recorded on the AEs section of the eCRF, except on the condition that, in the investigator's opinion, nausea and vomiting are caused by any reason different from lack of efficacy of study drug or meet the definition of serious AE.

Serious Adverse Event (SAE)

A serious adverse event is any event that suggests a significant hazard, contraindication, side effect, or precaution, whether or not it is considered to be associated with the study product. A SAE is an AE that meets any of the following criteria:

- Results in death. This includes any death that occurs during the conduct of a clinical study, including deaths that appear to be completely unrelated to the study drugs (e.g., car accident).

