- Is life-threatening. This includes any AE during which the subject is, in the view of the investigator, at immediate risk of death from the event as it occurs. This

definition does not include events that may have caused death if they had occurred in a more severe form.

- Requires inpatient hospitalization or prolongation of existing hospitalization
- Results in persistent or significant disability or incapacity
- Is a congenital anomaly or birth defect
- Other medical events that based upon appropriate medical judgment are thought to jeopardize the patient and/or require medical or surgical intervention to prevent one of the outcomes defining a SAE.

Unexpected Adverse Event

An Unexpected Adverse Event is any experience not previously reported (in nature, severity or incidence) in the current IB for oral NEPA FDC [16].

Expedited Adverse Event Reporting

Any serious and unexpected AE that the Investigator or the Sponsor considers to be at least possibly related to study drug is subject to expedited reporting to the appropriate Health Authorities. Events for which causality is unknown/unassessable or unreported by the Investigator are considered to be possibly related.

Non-serious Adverse Events

Non-serious adverse events should be included in tabulations in the end-of-study and do not need to be submitted separately.

Preexisting Condition

A pre-existing condition is one that is present at the start of the study. A pre-existing condition should be recorded as an AE if the frequency, intensity, or the character of the condition worsens during the study period.

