7.1.3 Reporting of Adverse Events

AE reporting has to be in accordance with the ICH E6 Guidance on GCP and ICH E2A Guidance on Clinical Safety Management. [27, 29]

During the course of the study, all AEs (including SAEs), irrespective of the relatedness to the study drugs, will be recorded in detail in the source records and transcribed onto the AEs pages of the eCRF. During each monitoring visit, the site monitor will review all AEs and perform Source Data Verification (SDV). The investigator will be responsible for ensuring that the correct information concerning all AEs is entered on the appropriate eCRF pages.

The reporting period for AEs is the period starting from the time of Informed Consent Form signature and lasting until Visit 5 or up to 14[+3] days post-dose. All non-resolved AEs (including SAEs) beyond this date will be documented on the eCRF as "ongoing".

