8.3.7 Safety Analyses

All AEs will be listed by SOC, described and summarized by frequency tables. Summaries will be made by treatment arm with respect to the percentage of patients having at least one occurrence of that event during the study and the total number of events.

For safety analysis, the laboratory data will be analyzed and described as follows: listings (including flag for values outside the normal range), count (number and percentage) of value below, within and above normal range, descriptive statistics for change from baseline values. Shift tables with respect to normal range (Low/Normal/High) will be presented. ECG data will be summarized highlighting differences from baseline for quantitative variables and frequencies of treatment emergent abnormalities. Vital signs will be summarized using descriptive statistics for observed values and change from baseline, in addition to being listed.

Safety analysis will be presented for the overall safety population and by strata.

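### The last sentence of section 6.3.4 lets new or worsened laboratory values attributed to a recorded disease go unrecorded as AEs, in conflict with its own preceding paragraph and with sections 7.1.1 and 7.1.3

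*Protocol*

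**What the plan says.** Two adjacent parts of protocol section 6.3.4 govern laboratory abnormalities.

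- The first says that when the investigator judges an abnormality clinically significant, "the etiology of the abnormality should be identified and the diagnosis should be recorded as an AE". If no cause is found, the abnormality itself is the AE. No exemption is given.
- The last sentence says that clinically significant values, including grade 3 or higher, "detected after screening, if not justified by an underlying disease already recorded in the medical history, are to be recorded as AEs".

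Section 7.1.1 defines an AE to include "any unfavorable and unintended sign (including an abnormal laboratory finding), symptom, or disease temporally associated" with use of the product, related or not. It adds: "This definition includes intercurrent illnesses or injuries, exacerbation of pre-existing conditions". On conditions present at study start it says: "A pre-existing condition should be recorded as an AE if the frequency, intensity, or the character of the condition worsens during the study period".

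Section 7.1.3 requires that "all AEs (including SAEs), irrespective of the relatedness to the study drugs, will be recorded in detail in the source records".

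For analysis, section 8.3.7 plans AE summaries by treatment arm. For laboratory data it plans flagged listings, counts below, within and above the normal range, and change from baseline. It adds: "Shift tables with respect to normal range (Low/Normal/High) will be presented".

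**The concern.** The last sentence of 6.3.4 asks the investigator to decide the cause of an abnormality before deciding whether to record it. Elsewhere the protocol records first and judges cause afterwards. The sentence does not mention the screening value, so it covers new and worsened findings as well as stable ones.

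The clause is open for every child. Inclusion criterion 4 requires confirmed malignant disease, and the current cancer is entered in the medical history at Visit 1 (section 5.2.1).

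Safety and tolerability is a secondary objective (section 2.2) in what section 1.4 describes as the first pediatric trial of netupitant. Below 12 months of age, the step from the lower to the higher dose in an age class follows review of 3 patients (section 3.1), so a single missing AE record would be a visible share of the AE evidence there. The SAP cannot repair this later, because an AE never entered has no causality assessment to analyse.

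**Working it through.** No arithmetic applies. The protocol states no figure on this point, and the result depends on no rate or sample size. The check is to apply each rule to the same finding.

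| Finding at Visit 4 (clinically significant) | 6.3.4, first rule | 6.3.4, last sentence | 7.1.1 with 7.1.3 |
|---|---|---|---|
| A. Chemistry value grade 3 or higher, attributed to the recorded cancer | AE | Need not be recorded | AE: new finding or worsening |
| B. Cytopenia present at screening, now worse, attributed to the recorded cancer | AE | Need not be recorded | AE: worsening |
| C. Cytopenia present at screening, unchanged, attributed to the recorded cancer | AE by its letter | Need not be recorded | Worsening rule not triggered |
| D. Cytopenia attributed to chemotherapy, new or worse | AE | AE: chemotherapy is not a disease in the history | AE |

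1. **A and B are the conflict.** The last sentence gives the opposite answer to the rule just before it and to 7.1.1. Section 7.1.3 adds to this: once 7.1.1 makes a finding an AE, it must be recorded whatever its relation to the study drugs.

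2. **A is not a remote case.** Inclusion criterion 7 limits ALT and AST to 2.5 times ULN and bilirubin to 1.5 times ULN at screening. Exclusion criterion 17 removes clinically relevant grade 3 or 4 non-hematological values and is re-checked on Day 1. In an eligible child, a clinically significant chemistry value of grade 3 or higher at Visit 4 will therefore generally be new or worse.

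3. **C is the only row where the exemption agrees with 7.1.1.** The sentence is not written so as to be confined to it.

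4. **The protocol already has a place for disease attribution.** In the causality scale of section 7.1.2.2, both the unlikely-related and the not-related categories name the patient's underlying disease as an alternative explanation. Those categories presuppose that such events have been recorded. Where 7.1.1 intends exceptions (planned procedures and admissions; nausea and vomiting as lack of efficacy) it lists them, and laboratory values are not among them.

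5. **What remains visible without an AE record.** Take a hypothetical ALT of 2.0 times ULN at screening and 20 times ULN at Visit 4. It is above range both times, so the normal-range shift table shows High to High. The change, 20 − 2.0 = 18 times ULN, does enter the change-from-baseline summary, and the value is flagged in the listing. The worsening is still in the data, but outside the AE tables and without a causality assessment.

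**The case against.** The strongest answer is that the two sections can be read together: a stable sign of recorded disease is not a new AE, and 7.1.1 takes over when it worsens. The last sentence of 6.3.4 neither mentions worsening nor claims to override section 7. That reading is sensible and is probably what was meant. It is not written, however. The sentence turns on cause, not on change, and for chemistry values the eligibility limits leave few stable high-grade findings for it to apply to.

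Other objections stand and limit the point. A reader might infer any of the following, and the protocol supports none of them:

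- **That toxicity is hidden.** The values remain in listings, counts and change-from-baseline summaries.
- **That the DSMB would not see them.** Section 9 provides study data and further information on request, and does not confine the board to AE tables. Its charter is a separate document.
- **That chemotherapy cytopenias are exempt.** The clause names a disease in the history, and Visit 4 falls on Day 6 to 8 after emetogenic chemotherapy, so chemotherapy is an obvious competing attribution that stays recordable.
- **That 92 patients are affected.** That number is how many could fall under the clause. It bites only when a clinically significant abnormality occurs and is attributed to recorded disease.
- **That the normal-range shift tables are an error.** They are not wrong, and section 8 leaves further detail of presentation to the SAP.

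**Conclusion.** The point holds as a conflict between recording rules. The last sentence of 6.3.4 permits omission of new or worsened, clinically significant laboratory abnormalities that the preceding rule, 7.1.1 and 7.1.3 require to be recorded, provided the investigator attributes them to a disease in the history. The clause is available for all 92 planned patients. The number of events affected cannot be derived from the protocol.

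The loss is confined to the AE record, the causality assessment and the AE tables by arm. The conclusion assumes that sites follow the last sentence as worded. If they all applied 7.1.1 in preference, nothing would be lost, but the protocol does not tell them which rule prevails. This warrants a correction to the text and is not evidence that the safety evaluation as a whole fails.

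**What to change.** Replace the last sentence of 6.3.4 with:

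> A clinically significant laboratory abnormality found after screening (including any value of grade 3 or higher) is recorded as an AE if it is new, or if it has worsened since screening in frequency, intensity or character, whatever its presumed cause. Attribution to underlying disease is entered in the causality assessment. Only an abnormality already present at screening and not worsened since then is exempt.

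Add a cross-reference to this rule in the preceding paragraph, so that row C is also treated consistently. The trigger should follow the worsening rule in 7.1.1. Requiring a higher CTCAE grade would be narrower and would miss a clinically significant worsening within a grade.

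The cost is a short text change and some additional AE records for disease-attributed abnormalities, which the causality assessment can separate. Chemotherapy-attributed abnormalities add nothing, since they are recordable already. A shift table by CTCAE grade from screening to Visit 4 would complement the normal-range table. It is optional and can be placed in the SAP. The change concerns recording only and leaves patient management untouched.

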7 ADVERSE EVENTS

7.1 Method of Assessment

7.1.1 Definition of Adverse Events

Adverse Event (AE)

As defined by the current ICH Guideline for Good Clinical Practice [27] an Adverse Event (AE) is:

Any untoward medical occurrence in a patient or clinical investigation subject administered a pharmaceutical product and which does not necessarily have to have a causal relationship with this treatment. An AE can therefore be any unfavorable and unintended sign (including an abnormal laboratory finding), symptom, or disease temporally associated with the use of a medicinal (investigational) product, whether or not considered related to the medicinal (investigational) product.

Within the scope of this study, such untoward medical occurrences would be considered as "AEs" even if the subject was not administered the study drugs but the subject (and/or subject's parent/guardian, as applicable) had already signed the Informed Consent/Assent Form.

This definition includes intercurrent illnesses or injuries, exacerbation of pre-existing conditions, and adverse events occurring as a result of drug withdrawal, abuse, medication errors, misuse or overdose. Adverse events observed during all periods of a clinical trial are to be recorded, including adverse events occurring during a period without trial medication.

Planned surgical interventions or planned hospitalizations scheduled prior to the Informed Consent but performed during the study should not be considered (serious) AEs.

Signs and symptoms considered as lack of efficacy (nausea and vomiting) and occurring during the study up to 5 days after the study drugs administration, will not be recorded on the AEs section of the eCRF, except on the condition that, in the investigator's opinion, nausea and vomiting are caused by any reason different from lack of efficacy of study drug or meet the definition of serious AE.

Serious Adverse Event (SAE)

A serious adverse event is any event that suggests a significant hazard, contraindication, side effect, or precaution, whether or not it is considered to be associated with the study product. A SAE is an AE that meets any of the following criteria:

- Results in death. This includes any death that occurs during the conduct of a clinical study, including deaths that appear to be completely unrelated to the study drugs (e.g., car accident).
- Is life-threatening. This includes any AE during which the subject is, in the view of the investigator, at immediate risk of death from the event as it occurs. This

definition does not include events that may have caused death if they had occurred in a more severe form.

- Requires inpatient hospitalization or prolongation of existing hospitalization
- Results in persistent or significant disability or incapacity
- Is a congenital anomaly or birth defect
- Other medical events that based upon appropriate medical judgment are thought to jeopardize the patient and/or require medical or surgical intervention to prevent one of the outcomes defining a SAE.

Unexpected Adverse Event

An Unexpected Adverse Event is any experience not previously reported (in nature, severity or incidence) in the current IB for oral NEPA FDC [16].

Expedited Adverse Event Reporting

Any serious and unexpected AE that the Investigator or the Sponsor considers to be at least possibly related to study drug is subject to expedited reporting to the appropriate Health Authorities. Events for which causality is unknown/unassessable or unreported by the Investigator are considered to be possibly related.

Non-serious Adverse Events

Non-serious adverse events should be included in tabulations in the end-of-study and do not need to be submitted separately.

Preexisting Condition

A pre-existing condition is one that is present at the start of the study. A pre-existing condition should be recorded as an AE if the frequency, intensity, or the character of the condition worsens during the study period.

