1.3.3 Clinical Data

1.3.3.1 Netupitant Alone or in Combination with Palonosetron

The oral formulation of netupitant, as single agent or in combination with other compounds, including the 5-HT₃ receptor antagonist palonosetron, has been investigated in 27 studies; 20 of them were conducted in healthy adult volunteers. A total of 1,939 adult subjects and patients received netupitant in combination with palonosetron and 206 adult subjects and patients received oral netupitant alone.

Oral netupitant was generally well tolerated at all dose levels tested. In healthy volunteers, the most frequently reported treatment-emergent adverse events (TEAEs) related to netupitant alone (not in combination) were headache, fatigue, somnolence,

nausea, asthenia, lethargy, diarrhea and abdominal pain. In phase 2 and phase 3 studies in cancer patients, the oral NEPA FDC showed a good safety profile and proved to be effective for the prevention of acute and delayed nausea and vomiting associated with initial and repeated courses of MEC and HEC. [16]

In the Phase 2 and Phase 3 studies, leading to oral NEPA FDC (Akynzeo[®]) approval, the type, frequency and intensity of AEs were comparable across treatment groups. There was no apparent dose-response effect and the safety profile of the oral NEPA FDC was similar to that of other dose combinations, to that of palonosetron alone and to that of aprepitant in combination with ondansetron or palonosetron (comparators in the Phase 2 and 3 studies). There were no clinically significant changes in laboratory parameters. No clinically significant changes in vital signs were reported across all studies. All data regarding electrocardiograms (ECGs) and QT intervals suggest no clinically relevant effects for QT prolongation in the Phase 1, Phase 2 and Phase 3 studies and in a thorough QTc study.

Further details are provided in the current IB of oral NEPA FDC. [16]

Pediatric studies have not been performed so far on the netupitant alone, or as a component in combination such as Akynzeo[®].

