4.11 Rescue Medication

Rescue medication should be administered to alleviate established, refractory or persistent nausea or vomiting and will be permitted on an as-needed basis.

Anti-emetic medications are not allowed as prevention of emesis, nor to increase the expected antiemetic effects of the study drugs, except for patients receiving HEC or MEC beyond Day 1.

Clinical Study Protocol

Rescue medication is defined as any medication taken to alleviate nausea or vomiting (i.e., with indication nausea or vomiting) during the period from start of emetogenic chemotherapy to 120 h later. The choice of rescue medication will be at the discretion of the Investigator. Investigator must ensure that rescue medication is made available to patients whenever needed.

Use of palonosetron or netupitant other than study drugs administration is not permitted.

Use of metoclopramide is not permitted as rescue medication.

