- The diary covering 120 h after start of emetogenic chemotherapy will be supplied to all patients. Patient or patient's parents/legal care holders have to record emetic episodes and use of any rescue medication.

5.2.3 Visit 3 (Day 2, 3, 4 and/or 5 depending on the PK sampling times)

The following procedures will be performed/data collected:

- Concomitant medications
- AEs recording
- PK sampling: a single blood sample will be collected from each patient within the time window from 24-48 h after netupitant administration. For pediatric patients ≥ 5 years, an additional PK sample will be collected from each patient within the time window from 72-96 h after netupitant administration.
- Review of patient diary and instructions. During the visit, after the diary has been reviewed, the patient will be asked to correct errors, omissions, or ambiguities, if any.

5.2.4 Visit 4 (final visit, Day 6, 7 or 8 depending on PK sampling times)

The following procedures will be performed/data collected:

- Concomitant medications
- Laboratory evaluations (hematology, serum chemistry and urinalysis; pregnancy test [(for female patients having reached menarche only])
- Full physical examination
- Vital signs (pulse rate, systolic and diastolic blood pressure; to be measured before PK sampling or at least 30 minutes after PK sampling)
- 12-lead ECG (single recording), before PK sampling or at least 30 minutes after PK sampling.
- AEs recording
- Check and retrieval of the completed patient diary
- PK sampling: a single blood sample will be collected from each patient within the time window from 120 to 168 h after netupitant administration.

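### Untreated, non-serious nausea put down to lack of efficacy in the first 5 days is recorded neither as an adverse event nor in the diary

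*Protocol*

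**What the plan says.** Section 7.1.1 (Definition of Adverse Events) sets an exemption from AE recording: "Signs and symptoms considered as lack of efficacy (nausea and vomiting) and occurring during the study up to 5 days" after study drug administration are not entered in the AE section of the eCRF. The same sentence carries two exceptions. The event is recorded if the investigator judges that "nausea and vomiting are caused by any reason different from lack of efficacy of study drug or meet the definition of serious AE".

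Section 6.2 (Efficacy Assessments) describes the efficacy instrument as a "paper diary, which will be used to record emetic episodes and use of rescue medication". Section 5.2.2 (Visit 2) repeats the two items: patients or parents are to "record emetic episodes and use of any rescue medication". An emetic episode is defined in 6.2 as "one or more continuous vomits (expulsion of stomach contents through the mouth) or retches", so nausea alone is not one. The PD endpoints in 6.2.2 are complete response, no emetic episodes and no rescue medication, each in three phases. None measures nausea.

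Section 4.11 links nausea to the diary indirectly: "Rescue medication is defined as any medication taken to alleviate nausea or vomiting (i.e., with indication nausea or vomiting) during the period" from the start of emetogenic chemotherapy to 120 h later.

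Section 1.3.3.1 lists nausea among the TEAEs most often related to netupitant alone in healthy volunteers: headache, fatigue, somnolence, "nausea, asthenia, lethargy, diarrhea and abdominal pain".

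**The concern.** Leaving efficacy failures off the AE pages is common and reasonable when the efficacy data hold them instead. Here the exemption names nausea and vomiting together, but the diary was built for vomiting, retching and rescue only. The two rules leave a class of events that neither record is designed to take.

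That matters for the secondary objective of safety and tolerability (section 2.2). Section 1.4 describes the first pediatric trial of netupitant, with two doses that differ 3-fold, and the synopsis says the results will support dose selection for a Phase 3 study. Nausea is both a possible drug effect and part of the indication, which is chemotherapy-induced nausea and vomiting. If its recording depends on a causal opinion given beforehand, the AE tables by treatment arm in section 8.3.7 show only the nausea that passed that filter.

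The filter also sits badly with the protocol's general AE rules. Section 7.1.3 asks for every AE whatever its relationship to study drug, and section 7.1.2.2 provides a category for events whose cause cannot be assessed. For early nausea the causal opinion decides whether the event is entered at all.

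**Working it through.** The main check is textual, because the plan states no figure on this point.

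**1. Where each kind of nausea in the first 5 days goes**

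| Nausea in the first 5 days | AE page | Diary |
|---|---|---|
| Attributed by the investigator to study drug or another cause | Yes (7.1.1, first exception) | Only if rescue was taken |
| Serious | Yes, plus SAE form (7.1.1, 7.1.4) | Only if rescue was taken |
| Attributed to lack of efficacy, non-serious, treated with medication | No | Indirectly, as rescue use; no onset, grade or duration of nausea required |
| Attributed to lack of efficacy, non-serious, untreated | No | No |

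Only the last row is wholly lost. If the same child also vomits or retches, the emetic episode is in the diary but the nausea is not.

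**2. Do the two time windows match?** The exemption runs 5 × 24 = 120 h from dosing. Dosing is 1 h (± 10 minutes) before chemotherapy (section 4.3), so it ends about 120 − 1 = 119 h after the start of chemotherapy. The diary runs to 120 h after that start. The windows nearly coincide, so the gap comes from content and not from timing. AE reporting continues to Visit 5 (section 7.1.3), so later nausea is recordable.

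**3. How much of netupitant exposure falls in the exempt period?** Cmax is reached at about 5 h (section 1.3.2.1) and the half-life is about 30 to 100 h (section 1.3.2.4). The period covers 120/100 = 1.2 to 120/30 = 4 half-lives, including the peak.

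**4. Can attribution separate the cases?** Every patient receives netupitant and then HEC or MEC about 1 h later. The healthy volunteers of section 1.3.3.1 had nausea judged related to netupitant. In this trial the same symptom has two candidate causes starting almost together.

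**5. Illustration of size.** No rate of nausea without emesis or rescue is given, so 20-40% is an assumption. The age from which a child can report nausea is not given either, so three cut-offs are shown. Planned numbers are from section 3.3.1, halved for the two dose groups.

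- Under 2 years: 12 + 12 + 8 + 8 + 8 = 48. Under 5 years: 48 + 12 = 60.
- Aged 2 or over: 92 − 48 = 44, or 22 per group. 0.20 × 22 = 4.4; 0.40 × 22 = 8.8.
- Aged 5 or over: 92 − 60 = 32, or 16 per group. 0.20 × 16 = 3.2; 0.40 × 16 = 6.4.
- Aged 12 or over: 16, or 8 per group. 0.20 × 8 = 1.6; 0.40 × 8 = 3.2.

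These counts are children with such nausea. How many would be lost depends on how many of the events are attributed to lack of efficacy.

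**The case against.** The strongest reply is that the gap is narrow and deliberate. Nausea judged to be a netupitant side effect has a cause other than lack of efficacy and must be recorded. Serious nausea is recorded. Treated nausea counts as rescue, has its own endpoint and makes the patient a failure for complete response. The primary objective and endpoint rest on complete response, and no secondary objective names nausea. With 40 of 92 planned patients under 12 months, endpoints based on observable events are defensible. Section 1.3.3.1 also reports no apparent dose-response effect for adverse events in the adult Phase 2 and 3 studies, which weakens the fear of a dose-related rise. Any dose comparison of nausea would be imprecise, with few children able to report, mixed HEC and MEC, and preventive antiemetics allowed after 24 h in multi-day regimens (section 4.10.1).

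Most of this stands, and it rules out stronger readings. A reader might infer that early nausea is captured nowhere; the two exceptions and the rescue definition show otherwise. A reader might infer that the AE rate for nausea will be close to zero in both groups; that predicts investigator behaviour, and the documents support only probable understatement. Applying an assumed rate to all 46 patients per group would ignore that 60 of 92 are under 5 years.

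The reply does not close the gap. Section 4.11 directs rescue to established, refractory or persistent symptoms, so milder nausea need not lead to it. The first exception needs a positive opinion of another cause, which is hard to form here. The adult finding of no dose-response does not replace recording in the first pediatric study.

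**Conclusion.** The point holds in a limited form. Non-serious, untreated nausea that the investigator attributes to lack of efficacy in the first 5 days after dosing is recorded neither as an AE nor as efficacy data. Nausea attributed to another cause and serious nausea are recorded. Treated nausea is visible only through rescue use.

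The likely consequence is an AE table that understates nausea over the days of highest exposure, and no direct measure of the nausea part of the indication. The direction follows from the recording rules together with the difficulty of attribution; its extent cannot be derived from the documents. Under the assumed 20-40% rate, roughly 2 to 9 children per dose group would have such nausea, depending on whether reporting starts at age 12, 5 or 2.

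The primary PK/PD endpoint does not change, because complete response is defined without nausea. The protocol supports no claim that the dose comparison of efficacy is biased. This is an inexpensive improvement to the secondary safety and tolerability objective.

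**What to change.** Reword the exemption in section 7.1.1 so that it covers only what the diary captures: emetic episodes within 120 h of the start of HEC or MEC. Then choose one of two ways to record nausea in that period:

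- enter it on the AE page with its CTCAE grade and relationship category, including the existing category for events that cannot be assessed; or
- add one daily yes/no nausea line to the existing diary for children able to report it, and state in section 6.2 who that is.

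Either way, tabulate nausea descriptively by dose group, with the number of children able to report as the denominator for the diary item.

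The cost is one sentence or one diary line. The diary is already kept to 120 h and reviewed at Visit 3, so no visit is added. The downside is more AE entries under the first option, mostly chemotherapy-related, and a dose comparison that remains imprecise under both. If neither is adopted, the protocol should at least say that nausea AE rates for the first 5 days exclude nausea attributed to lack of efficacy.
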